1. AIM OF THE STUDY

Aim of the study is to evaluate the efficacy and the safety of the deep injection of Profhilo Structura® in acne scars of the face (ice picks, rolling, boxcars).

It is also aim of this study to evaluate volunteer's satisfaction with the treatment effects and physicians satisfaction with the study products use.

2. MATERIALS

- Profhilo Structura® (IBSA Farmaceutici Italia S.r.l. see Appendix 1)
- -25 G, 40 mm Magic Needles (Cannula) (with 23 G Needle for entry point)
- -25 G Terumo Needle
- Digital camera
- Primos compact portable (GFMesstechnik)

3. STUDY DEVICE

ProfhiloStructura® (IBSA Farmaceutici Italia S.r.l.) is a resorbable medical device 2 ml non-pyrogenic pre-filled syringe, containing 2 ml of 4,5% hyaluronic acid for intradermal use (45 mg H-HA + 45 mg L-HA dissolved in 1,5 ml of saline buffered sodium chloride – IBSA Farmaceutici Italia S.r.l. – ITALY. The principal component of the medical device is Hyaluronic Acid of non-animal origin, produced by bacterial fermentation.

To note that in the clinic preliminarily tested 8 subjects volunteers with the product under study, with no adverse events occurrence.

4. STUDY DESIGN

[figure not shown]
4.1. Study plan

Open clinical trial, conducted by 1 center under dermatological control.

3 visits will be performed during the study:

- T0 (baseline) clinical and instrumental evaluations, followed by the 1st injection procedure
- T1 (1 month after the 1st injection procedure) clinical and instrumental evaluations, followed by the 2nd injection procedure
- T2 (3 months after the 2nd injection procedure) clinical and instrumental evaluations.

DermIng S.r.l., Clinical Research and Bioengineering Institute [name] [contact]– www.derming.com

4.2. Experimental design

The 1st treatment will be performed during T0 visit, after the basal evaluations planned by the study procedure. Treatment of acne scars of the face by using a subcision+injection technique: the needle (25 G) or cannula (25 G) (wider areas are treated with the cannula) is inserted into the skin and made to move with a back-and-forth motion in order to detach scar collagen bundles. Then the product is injected. The 2nd treatment will be performed after 4 weeks (1 month from T0). Results of the study will be elaborated after the completion of the clinical phase.

4.3. Investigators

The study will be conducted by and under the supervision of a dermatologist.

5. RECRUITMENT OF THE VOLUNTEERS

5.1. Characteristics of the population

The study will be conducted on Caucasian of both sexes volunteers aged >18 years

5.2. Number of volunteers

A total of 30 subjects will be enrolled in the trial.

5.3. Inclusion criteria

Volunteers with the following characteristics will be included in the study:

- caucasian subjects of both sexes;
- age >18 years
- asking for acne scars treatment;

DermIng S.r.l., Clinical Research and Bioengineering Institute	
[name]	
[contact]— www.derming.com	
Test code	
E0222	

- presenting acne scars (ice picks, rollings, boxcars);
- available and able to return to the study site for the post-procedural follow-up examinations;
- agreeing to present at each study visit without make-up;
- accepting to not change their habits regarding food, physical activity, make-up use, face cosmetic and cleansing products;
- accepting not to expose their face to strong UV irradiation (UV session, or sun bathes) during the entire duration of the study, without appropriate sun protection;
- accepting to sign the Informed consent form.

5.4. Exclusion criteria

5.4.1. Dependent on the volunteers' characteristics:

- smokers;
- performing in the 6 month before the trial beginning HA injections, radiofrequency treatment, toxin treatment;
- contraindication or know allergy to the devices' components or to the treatment;
- participation in a similar study actually or during the previous 3 months
- known pregnancy
- -occurrence of pregnancy during the study

5.4.2. Dependent on a clinical condition

5.4.2.1. Dermatological disease

- Dermatitis;
- presence of cutaneous disease on the tested area, different from those under study
- recurrent facial/labial herpes;
- clinical and significant skin condition on the test area (e.g. active eczema, psoriasis, severe rosacea, scleroderma, local infections and severe acne).

5.4.2.2. General disease

- Diabetes, coagulation disorders, connective tissue disorders, lipodystrophy or other systemic disease;
- HIV and/or immunosuppressive disease;
- cancerous or precancerous lesions in the either right or left midface;
- severe allergies manifested by a history of anaphylaxis, or history or presence of severe multiple allergies;
- alcohol or drug abusers.

5.4.3. Dependent on a pharmacological treatment

- Anti-inflammatory drugs, anti-histaminic, topic and systemic corticosteroids, narcotic, antidepressant, immunosuppressive drugs (with except of contraceptive or hormonal treatment starting more than 1 year ago);
- assumption of drugs able to influence the test results in the investigator opinion.

The use of other drugs, not mentioned above, can be authorized by the Investigator. The trade name, the dosage, the start and stop date of the therapy will be reported on Case Record Form (CRF).

5.4.4. Restrictions

The volunteers accept to respect the rules fixed in the list of recruitment criteria and not to deviate from their normal life habits. Moreover, the month preceding the inclusion visit and during the entire period of treatment, sun and UV light exposure, will be avoided. In the case of UV exposure, very high protection cream must be used.

DermIng S.r.l., Clinical Research and Bioengineering Institute [name] [contact]— www.derming.com

6. CASE RECORD FORM

For each volunteer a Case Record Form is filled and a progressive number is assigned to each one. Personal data, subject's history, inclusion/exclusion criteria, clinical evaluations are registered in the CRF.

7. SAMPLE ACCEPTANCE, IDENTIFICATION AND APPLICATION

The Sponsor supplies directly each study center and samples will be save as indicated by the Sponsor. The products to be tested are recorded, with a reference number, in the Human Studies Record Book together with additional information such as the arrival date, the test requested, Sponsor's name, the product code, the order number and any other information reported on the container.

During the twelve months following the issue date of the report, a counter-sample will be kept in the same conditions as those described above.

8. TREATMENT EVALUATION

8.1. Inclusion visit

Each volunteer is submitted to a careful clinical examination in order to check the selection criteria.

8.1. Clinical evaluations

Clinical assessment will be performed during the basal visit (T0) and then at T1 (1 month, 2nd aesthetic procedure) and T2 after 3 months since the 2nd aesthetic procedure. The grade of scarring will be evaluated by Goodman and Baron scale:

TABLE 1. Goodman and Baron Grading Scale of Postacne Scarring

GRADE	SEVERITY GRADE	CHARACTERISTICS	EXAMPLES OF
			SCARS/LESIONS
1	Macular	Erythematous, hyper-	Erythematous, hyper-
		or hypopigmented flat	or hypopigmented flat
		marks visible to	marks
		patient or observer	
		irrespective of	
		distance	a a
2	Mild	Mild atrophy or	Mild rolling, small soft
		hypertrophy that may	papular
		not be obvious at	
		social distances of	
		50cm or greater and	
		can be adequately	
		covered by makeup,	
		the normal shadow of	
		shaved beard in males,	
		or normal body hair if	
		extrafacial	
3	Moderate	Moderate atrophic or	More significant
		hypertrophic scarring	rolling, shallow,
		that is obvious at	boxcar, mild-to-
		social distances of	

DermIng S.r.l., Clinical Research and Bioengineering Institute
[name]
[contact]– www.derming.com
Test code
E0222

		50cm or greater and is not able to be covered by makeup, the normal shadow of shaved beard in males, or normal body hair if extrafacial, but is still able to be flattened by manual stretching of the skin	moderate hypertrophic or papular scars
4	Severe	Severe atrophic or hypertrophic scarring that is obvious at social distances of 50cm or greater and is not able to be covered by makeup, the normal shadow of shaved beard in males, or normal body hair if extrafacial, and is not able to be flattened by manual stretching of the skin	(deep boxcar), ice pick, bridges and tunnels, gross atrophy, dystrophic scars, significant

8.2.3. Non-invasive instrumental evaluations

A measurement of the skin surface affected by acne scars is taken thanks to Primos compact portable device (GFMesstechnik); Primos software is able to measure skin principal profilometric parameters in vivo or on skin replicas, according to the law DIN EN ISO 4228; moreover, the software compares directly the different images obtained at the times foresee by the protocol.

As a measuring method Primos compact uses a digital stripe projection based on micro mirrors which allows for fast and highly precise measuring data acquisition (the speed of under 70ms for the measuring data admission provide perfect results of measurement).

An assortment of different measuring fields, realized by means of different precise recording optics ensures a wide spectrum of measuring possibilities with ranges up to micrometres.

The portable probe assures a constant distance from the skin as well as a fixed illumination angle of incidence; in this way is possible to acquire standardized and reproducible measurements.

8.2.3 Digital images

Clinical pictures are taken at the level of treated scars at each considered evaluation time, in order to compare them and assess the efficacy of the treatment.

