12.3. Clinical data

The statistical analysis of clinical data is carried out with not parametric test.

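### Photographs are used to judge efficacy in an open, single-arm trial, but no masking to visit, image order or scored reading is specified; a random-order masked reading would cheaply reduce reader bias.

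*Combined protocol and SAP*

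**What the plan says.** Section 4.1 describes the design: "Open clinical trial, conducted by 1 center under dermatological control". It also states "3 visits will be performed during the study", namely T0, T1 and T2. Section 5.2 gives the size: "A total of 30 subjects will be enrolled in the trial". Under section 4.2 all subjects receive the same treatment, and results are worked up once the clinical phase is over.

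On the photographs, section 8.2.3 (Digital images) says: "Clinical pictures are taken at the level of treated scars at each considered evaluation time, in order to compare them and assess the efficacy". The plan says nothing more about reading them. It gives no reader, scale, image order or labelling rule.

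On staff, section 4.3 says only: "The study will be conducted by and under the supervision of a dermatologist". Section 8.1 (Clinical evaluations) adds a live clinical grade: "The grade of scarring will be evaluated by Goodman and Baron scale". It does not name the grader. The profilometry in the other section numbered 8.2.3 is compared by software: "the software compares directly the different images obtained at the times foresee by the protocol".

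In the statistical section, 12.3 says: "The statistical analysis of clinical data is carried out with not parametric test". Section 12.5 expresses each time point against T0. Nothing in section 12 deals with the photographs specifically.

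**The concern.** Comparing before and after photographs is a human judgement. A reader who knows which picture is the later one, in a study where every subject was treated, may lean towards the later picture. With no concurrent untreated group, nothing in the data shows how large that lean is. A favourable photographic result could then be reported as efficacy when part or all of it is expectation.

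This is more than a missing detail because the remedy is already within reach. The pictures are collected for every subject at every visit, and the results are prepared only at the end. Both images of a pair can therefore be shown side by side with the visit hidden. No new visit, procedure, device or subject is needed.

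**Working it through.** **The plan's own figure.** The only number to reproduce is the enrolment of 30 (section 5.2). It cannot be reproduced, because the documents give no significance level, power, effect size, variability or dropout for it. The 5% in section 12.4 is the threshold of the normality test, not an efficacy level. What follows is an illustration, not a recalculation.

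**Inputs**
- From the plan: n = 30 subjects, with pictures at T0 and T2.
- Assumed: one forced choice per T0/T2 pair, a two-sided 5% level, independent subjects, and no true change in scarring.
- Assumed: the probability p that T2 is picked is 0.50 if the order is effectively hidden. It is 0.55 to 0.70 if the visit is known and the reader leans towards T2. The documents give no value for this lean.

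**Step 1: cut-off.** With X ~ Binomial(n, p), P(X ≥ r) = Σ C(n,k) p^k (1−p)^(n−k), summed over k = r to n. For n = 30 and p = 0.5, P(X ≥ 21) = 0.0214, so the two-sided p-value is 2 × 0.0214 = 0.043. At 20 picks it is 2 × 0.0494 = 0.099. The test therefore favours T2 at 21 or more picks.

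**Step 2: chance of a favourable result with no true change.** The same is shown for 27 and 24 readable pairs, each with its own cut-off.

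| P(T2 picked) | n = 30, cut-off 21 | n = 27, cut-off 20 | n = 24, cut-off 18 |
|---|---|---|---|
| 0.50 (masked) | 2.1% | 1.0% | 1.1% |
| 0.55 | 6.9% | 3.4% | 3.6% |
| 0.60 | 17.6% | 9.5% | 9.6% |
| 0.65 | 35.8% | 21.8% | 21.1% |
| 0.70 | 58.9% | 41.1% | 38.9% |

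**Step 3: can a masked reading still detect something?** If T2 is truly picked 75% of the time, P(X ≥ 21 | 30, 0.75) = 80.3%. This needs all 30 pairs to be readable. With 27 readable pairs and a cut-off of 20 it is 64.3%.

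**Step 4: missing pictures.** Suppose a fraction m of T2 pictures is missing and each is counted as not favouring T2, with all 30 kept in the denominator. The chance level becomes 0.5 × (1 − m): 45% at m = 10% and 40% at m = 20%. With 3 of 30 missing, reaching 21 picks at a true 75% preference has probability P(X ≥ 21 | 27, 0.75) = 47.1%, not 80.3%. Under that rule the 50% reference no longer applies, so it suits a sensitivity analysis and not the main one.

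**The case against.** A reader might infer that the treating team compares the pictures knowing both visit and treatment, and that it also assigns the clinical grade. The documents do not say so. They name no reader of the photographs and no grader, and section 4.3 says only that a dermatologist conducts and supervises the study. What they support is that masking is not specified. Knowledge of treatment is not a separate issue, since everyone is treated. Only the visit can be hidden.

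A reader might also infer that an existing endpoint is being distorted. No scored photographic endpoint exists: section 8.2.3 gives no score and section 12 no analysis. The proposal therefore defines a reading as well as masking one. That objection stands, and it is why the fix has to supply the question, the contrast and the statistic.

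Three further objections stand:
- Masking would be incomplete. A dermatologist who treated the subjects may recognise them, and the section on digital images sets no standard for lighting, angle or distance, so differences between images may reveal the visit. Bias would be reduced, not removed.
- The live Goodman and Baron grade would stay unmasked, so any optimism there is untouched. Inflation estimated for that grade cannot be credited to this fix.
- A forced choice shows direction, not size of benefit. Software-compared profilometry at each visit is already less exposed to reader expectation.

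None of these makes an unmasked reading preferable. Profilometry does not make the photographic judgement reliable.

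**Conclusion.** The point holds as a low-cost improvement to one assessment. The plan uses photographs to judge efficacy in an open, single-arm study and specifies no masking to visit, no image order and no scored reading.

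Under the assumptions above, with 30 readable pairs and no true change, the false favourable rate is 2.1% when masking works and 6.9% to 58.9% when knowing the visit lifts T2 picks to 55% to 70%. The size depends on that assumed lean, which the documents do not give. The direction does not.

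The gain is limited to reader expectation. Masked order does not replace a control, does not deal with regression to the mean or natural change, and does not alter the completers-only population in section 12.2. The 80% power at a 75% preference should be quoted only for 30 readable pairs.

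**What to change.** **Section 8.2.3 (Digital images).** State that, after the last T2 visit, visit labels are stripped from each subject's T0 and T2 photographs and left/right order is randomised. A site dermatologist then chooses the image with less visible scarring. If someone already on staff did not treat the subject, that person is preferred as reader.

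**Section 12.** Report the number of T2 picks out of readable pairs with an exact 95% interval, against a 50% chance level. For example, 21 of 30 is 70%. Its Clopper–Pearson limits, solving P(X ≥ 21 | p) = 0.025 and P(X ≤ 21 | p) = 0.025, are 50.6% and 85.3%. Add a sensitivity analysis that counts missing T2 pictures as not favouring T2, and say that the chance level under that rule is below 50%.

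**Section 8.1 (Clinical evaluations).** Keep the live Goodman and Baron grade and report it as unmasked. Grades 3 and 4 are told apart by manual stretching of the skin, so they cannot be read from photographs.

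**Cost.** A paragraph in each of sections 8 and 12 and a few hours of staff time. The report should say that masking was partial.

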8.3. Standard conditions for the treatment evaluations

8.3.1. Volunteers

During 3 hours before the visit the volunteer must not smoke, drink coffee or alcohol. Any cosmetic product can be used on the skin test areas from 2 hours before each visit.

DermIng S.r.l., Clinical Research and Bioengineering Institute	
[name]	
[contact]– www.derming.com	
Test code	
E0222	

All study evaluations are performed at room temperature; no temperature/humidity recording is required.

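### Section 8.3.1 literally permits cosmetics on the test skin before each visit, very probably 'any' written for 'no', and for make-up it contradicts the criterion in 5.3

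*Combined protocol and SAP*

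**What the plan says.** Section 8.3 sets the standard conditions for the treatment evaluations. Its paragraph on volunteers (8.3.1) contains two rules. The first is "During 3 hours before the visit the volunteer must not smoke, drink coffee or alcohol". The second, directly after it, is "Any cosmetic product can be used on the skin test areas from 2 hours before each visit".

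Two inclusion criteria in 5.3 bear on the same matter. A volunteer is included on "agreeing to present at each study visit without make-up", and also on "accepting to not change their habits regarding food, physical activity, make-up use, face cosmetic and cleansing products".

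The measurements concerned are described under the two headings numbered 8.2.3. For Primos profilometry, "the software compares directly the different images obtained at the times foresee by the protocol". Photographs of the treated scars are taken at each evaluation time "in order to compare them and assess the efficacy of the treatment". Section 12.5 reports results relative to T0. Section 4.1 describes the study as "Open clinical trial, conducted by 1 center under dermatological control", and no control group is planned.

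**The concern.** The purpose of 8.3 is to put volunteer and skin in a known state before measurement. A sentence in that section allowing any cosmetic on the measured area, up to the visit itself, does the reverse.

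Primos reads the surface of the skin, so any product lying there becomes part of what is measured. The same holds for what the camera records. Each later visit is set against the same volunteer's T0. If there were more or less product on the skin at T1 or T2 than at T0, the difference would enter the recorded change. With no control arm, no comparison group would be available to offset it. The possible results are extra noise, or bias if use shifted systematically between visits.

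**Working it through.** The protocol gives no figure to reproduce on this point. The check sets the passages side by side.

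1. **The sentence alone.** Taken as English, it permits every cosmetic on the test areas during the 2 hours before a visit.

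2. **Its neighbour.** The preceding sentence is a prohibition covering the 3 hours before the visit. A permission would be out of place as the second item.

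3. **The time limit.** Section 5.3 already leaves the usual face cosmetics in place. A permission starting 2 hours before a visit would add nothing to that. As a prohibition, the limit has an obvious use: it defines a product-free window.

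4. **The same word elsewhere.** Section 13.1 literally requires subjects to be enrolled ahead of ethics approval, yet it closes by saying that the study starts only once approval has been given. There *any* plainly stands for *no*. Section 13.3 literally has the sponsor declare that the components are seriously toxic, where the negative must be meant. Usage alone does not settle the matter, because the next sentence of 13.1, on signing consent, uses *any* for *every*. Points 2 and 3 carry the inference, and the pattern supports it.

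5. **Against 5.3, by type of product.**
   - *Make-up.* A volunteer who uses the permission and arrives wearing make-up breaks the criterion. The two texts contradict each other, and the criterion is the more specific rule for make-up.
   - *Creams and other products that are not make-up.* Section 5.3 sets no visit-day rule for these, so there is no contradiction. Equally, no visible text restricts them before a visit. The only sentence that addresses them is the one in 8.3.1, which permits them.

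6. **Consequence for a change from T0.** Suppose, as a simplifying assumption, that product on the skin shifts a reading additively by *f*. For one volunteer at visit *t*:

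   recorded change = change on clean skin + (*f* at *t* − *f* at T0)

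   The bracket is zero when no product is used, or when its effect is the same at both visits. Otherwise its size and sign are unknown. The documents give neither the effect of a cosmetic film on Primos output or photographs nor the frequency of use, so no number can be put in.

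**The case against.** The best reply is that the intent can be recovered. The section title, the prohibition before it and the 2-hour limit all point to a restriction. Even if the slip lay in *from* (for *until*) rather than in *any*, the result would be the same: nothing on the skin in the last 2 hours. Harm arises only if the site follows the reading that was almost certainly not meant, and nothing in the documents suggests that it would. For make-up, 5.3 already supplies the right rule. For everything else, the unchanged-habits criterion works against differences between visits.

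Most of this stands, and it keeps the point small. It does not remove the error. This is an operative rule, not background text, and for products other than make-up no other visible text supplies the restriction.

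A reader might infer more than the documents support:

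- *That the results will be biased.* Bias needs product use that differs systematically between visits, and no passage indicates that. The lack of a control arm means that a difference would not be offset. It is not evidence that one would occur.
- *That the number of occasions measures impact.* With 30 subjects the rule applies at up to 30 × 3 = 90 subject-visits and bears on up to 30 × 2 = 60 comparisons with T0. Any visit-level rule in the protocol would give the same counts, so they describe scope only.
- *That 5.4.4 also conflicts.* It says "In the case of UV exposure, very high protection cream must be used", but that is conditional, and the section otherwise asks volunteers to avoid sun and UV light. No visit-day clash with the intended rule is shown.
- *That the missing check for product in the visit lists (10.1 to 10.3) is a second defect.* Those are short lists of activities, the CRF form itself is not available, and no 8.3.2 heading is visible between 8.3.1 and 8.3.3. Silence there shows little.

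**Conclusion.** The sentence in 8.3.1 is wrong as written. It states the reverse of its very probable intent, and for make-up it contradicts 5.3. The point is minor, a matter to consider rather than a threat to the trial.

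Confidence is high for the wording only. That *no* was meant remains an inference, though a strong one. The consequence is conditional on the site following the literal text and on product use differing between visits. Its size cannot be derived from the documents, and the two criteria in 5.3 limit it: one for make-up, the other for differences in habits. The statement that nothing else restricts other products covers the visible text only. The point concerns Primos and the photographs, and makes no claim about the Goodman and Baron grade or the T2 questionnaire.

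**What to change.** In 8.3.1, open the sentence with *No cosmetic product may be used* in place of its present permission, and leave the rest of it unchanged. Align it with the no-make-up criterion in 5.3, so that the two sections give one rule for visit days.

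The cost is one reworded sentence, with no added visits, procedures, staff or subjects. This point calls for no new CRF item and no change to 5.4.4. The like slips in 13.1 and 13.3 are separate copy-edits that can be made in the same revision.
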